#### 9.1.2.2 8 mg Titration and Maintenance Period

In the 8 mg Titration Period (4 weeks), subjects will be administered 6 mg QD of perampanel for 2 weeks and then will be up-titrated to 8 mg QD and will continue for 2 weeks. If subjects have no safety issues at the end of the Titration Period, they will start the 8 mg Maintenance Period for 26 weeks.

If subjects don't tolerate 8 mg administration of perampanel, they will be able to down-titrate to 6 mg in accordance with the investigators' discretion. After the down-titration, subjects could continue the study with 6 mg QD.

If subjects experience the occurrence of seizures or could not continue 8 mg (or 6 mg) dosing due to intolerable adverse event during the 8 mg Maintenance Period, they will end the Treatment Phase.

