#### 9.1.3 Extension Phase

When subjects complete the Treatment Phase and agree to continue receiving the perampanel monotherapy, they could enter the Extension Phase. Subjects who complete the 26-week Maintenance Period will continue the last dose of the Maintenance Period. Subjects who end the Treatment Phase due to insufficient efficacy or safety issue before the completion of the 26-week Maintenance Period will adjust their appropriate dose (within 4 – 8 mg of perampanel) and continue the Extension Phase. Subjects will be allowed to adjust within 2 – 8 mg of perampanel with investigators' consideration for their condition of the seizures and/or tolerability. During whole study period, the maximum dose of perampanel is 8 mg QD. The dose will be increased at intervals of 1 week or more in increments of 2 mg.

If subjects need to take other antiepileptic drugs (AEDs) or withdraw perampanel because of insufficient efficacy or tolerability issue of perampanel by the investigator's judgement, they will discontinue the study.

Once perampanel monotherapy is approved in each country, an End of Study Visit should be conducted promptly, and the subject would have to switch to the commercial product. If a subject does not switch to the commercial product promptly, an End of Study Visit and a Follow-up Visit should be conducted for the subject.

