- d: Adverse events will be collected from the time the subject signs the informed consent/assent form through the last visit. Serious adverse events will be collected for 28 days after the subject's last dose.
- e: At Visit 4a, if a subject is down-titrated to 6 mg due to intolerability after up-titrated to 8 mg, the subject will enter the Maintenance Period with 6 mg. After Visit 4a, if a subject experiences seizures or could not continue dosing due to intolerable adverse event, the investigator will end the 8 mg Maintenance Period.
- f: Only potentially pregnant female subjects will undergo the urine β-hCG pregnancy test.
- g: Collect blood samples if subjects are withdrawn from the study before Visit 7a.
- h: Only subjects whose QTcF is measured as >450 ms at any Visit will undergo additional 2 consecutive ECGs at 5- to 10-minute intervals (a total of 3 ECGs) to confirm the abnormality.
- i: At an unscheduled Visit, only the procedures/assessments that the investigators etc. has judged as necessary according to the subject's conditions will be performed.

- j: If a taper is decided based on the judgment of the investigator, dispensing the study drug should be needed.
- k: The visit for transition from the 8 mg Treatment Phase to the Extension Phase before completion of the 8 mg Treatment Phase

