8.2 Efficacy Data Handling

Definition of Seizure-Free status

The definition of seizure-free for perampanel 4 mg will be as follows;

The subjects who completed the 4 mg Treatment Phase with no seizures will be treated as Seizure-Free status. The subjects who had any seizures will also be treated as Seizure-Free status only if the seizure(s) appeared after the Day 183 (ie, the target visit date of the 26th week of 4 mg Maintenance Period). Day 1 is the date of first dose of study drug in the 4 mg Maintenance Period. Otherwise, subjects will be regarded as non-Seizure-Free for the evaluation of perampanel 4 mg.

The definition of seizure-free for perampanel total (regardless of doses) will be as follows;

The subjects who completed the Treatment Phase of the last evaluated dose (ie, 4 or 8 mg) with no seizures will be treated as Seizure-Free status. The subjects who had any seizures will also be treated as Seizure-Free status if the seizure(s) appeared after the Day 183 (ie, the target visit date of the 26th week of Maintenance Period for the last evaluated dose). Day 1 here is the date of first dose of study drug in the Maintenance Period of the last evaluated dose. If subjects who were titrated up to 8 mg but down-titrated to 6 mg due to tolerability issue continued the study and completed the Maintenance Period with no seizure, those will also be treated as Seizure-Free status. Otherwise, subjects will be regarded as non-seizure-free.

Handling of seizure frequency

- **Baseline**

Baseline seizure frequency will be composed of the record based on the interview at visit 1 and the dispensed diary. Baseline seizure frequency will be calculated as the number of seizures per 12 weeks (see below).

$\frac{\text{Sum of seizures during baseline}}{\text{the number of days (84 days plus the study days during the Pretreatment Phase)}} \times 84$

Study days during the Pretreatment Phase will be the period between the date of obtaining informed consent and the date of first study drug dosing (ie, the date of study drug dispensing for visit 2).

- **Post-Baseline (Maintenance Period and Extension Phase)**

Post-baseline seizure frequency will be composed of the dispensed diary. Post-baseline seizure frequency will be calculated as the number of seizures per 12 weeks (see below). The Follow-up Phase will not be included in this analysis.

$\frac{\text{Sum of seizures during post-baseline}}{\text{the number of study days during post-baseline}} \times 84$

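### The late-seizure sentence of the any-dose seizure-free definition has no completion or on-dose condition, so an early 8 mg leaver with a first seizure after Day 183 counts as a success and one with no seizure as a failure

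*SAP*

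**What the plan says.** SAP 8.2 gives three routes to seizure-free status regardless of dose.

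- Completion without seizures: "The subjects who completed the Treatment Phase of the last evaluated dose (ie, 4 or 8 mg) with no seizures will be treated" as seizure-free.
- Late seizure: "The subjects who had any seizures will also be treated as Seizure-Free status if the seizure(s) appeared after the Day 183". The clock is set by "Day 1 here is the date of first dose of study drug in the Maintenance Period of the last evaluated dose". No end date is given.
- Down-titration from 8 mg to 6 mg, for subjects who "continued the study and completed the Maintenance Period with no seizure, those will also be treated as Seizure-Free status".

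A closing sentence makes everyone else non-seizure-free. The 4 mg definition ends in the same way ("Otherwise, subjects will be regarded as non-Seizure-Free").

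The Protocol lets a subject leave 8 mg Maintenance early and stay in the study. Section 9.1.2.2 says that subjects who have seizures or cannot continue dosing "due to intolerable adverse event during the 8 mg Maintenance Period, they will end the Treatment Phase". Section 9.1.3 then provides for the Extension: "Subjects who end the Treatment Phase due to insufficient efficacy or safety issue before the completion of the 26-week Maintenance Period will adjust" their dose and continue. Table 4 has an early transition visit for this, described in footnote k as "The visit for transition from the 8 mg Treatment Phase to the Extension Phase before completion of the 8 mg Treatment Phase". Table 5 keeps the seizure diary going in the Extension.

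SAP 5.4.2 makes the any-dose rate, with its lower 95% limit set against 40%, the key secondary efficacy analysis.

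**The concern.** The first and third routes ask for completion. The second asks only when the seizures occurred. It does not require that the subject completed the Maintenance Period, was still in it on Day 183, or had the seizure while in the Treatment Phase. Early transition to the Extension produces subjects who can meet the second route without having been observed on the evaluated dose for 26 weeks.

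For these subjects a seizure turns a failure into a success. The status of one subject can also improve between an earlier and a later data cut, because SAP 5.4 uses the data available at the cutoff. For non-completers the error runs one way: it only adds successes.

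At stake are the key secondary rate and the analyses that reuse the 26-week any-dose status: the subgroups in SAP 5.3.4, the seizure-type and simple-partial-history summaries in SAP 5.4.3, and the plot of concentration by seizure-free status in SAP 5.5.1.1.

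**Working it through.** **1. The plan's own figures.** Inputs from SAP Section 4: 72 mITT subjects, threshold 40%, expected rate 60%, Clopper-Pearson limits. The exact 95% interval for 38/72 is 40.65% to 64.67%, which matches the table (40.7, 64.7). With success defined as at least 38 of 72, exact power at 60% is 91.4%, which agrees with the stated figure of more than 90%. The point below does not alter sample size or power.

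**2. What Day 183 is.** In Protocol Table 4, 8 mg Maintenance starts on Day 29 of the 8 mg phase and Visit 9a falls on Day 211: 211 − 29 + 1 = 183. So Day 183 is the target date of the final Maintenance visit, which has a window of ±7 days.

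**3. The rule applied literally.** Days count from the first dose of 8 mg Maintenance; a late seizure is read as a first seizure after Day 183.

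| Course | Route met | Score |
|---|---|---|
| Completes 8 mg Maintenance, no seizure | First | Seizure-free |
| Seizure on Day 100 | None | Non-seizure-free |
| Stops on Day 60 for an adverse event, enters Extension, never has a seizure | None | Non-seizure-free |
| Same subject, first seizure in Extension on Day 240 | Second | Seizure-free |

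The last two rows differ only in the seizure.

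**4. Whether another section closes the gap.**
- SAP 8.1 keeps Follow-up data out of the summary tables, and SAP 8.2 confines Titration and Follow-up seizure data to listings. Neither excludes Extension seizures.
- SAP Section 3 scores subjects still continuing the 8 mg Treatment Phase at the early analysis as non-seizure-free. It does not cover those already in the Extension.
- SAP 5.4.2 refers to the 26-week Maintenance Period of the last evaluated dose but adds no completion condition.

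**5. Size per subject.** 1/72 = 1.39 percentage points. An assumed 1 to 5 such subjects would add 1.4 to 6.9 points (5/72 = 6.94%).

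**6. How many subjects.** The documents do not say. As an illustration only, assume 20 to 29 escalate to 8 mg, 5% to 20% of these stop without a seizure and enter the Extension, and 20% to 40% of those have a first seizure after Day 183.
- Low: 20 × 0.05 × 0.20 = 0.2 subjects, or 0.3 points.
- Middle: 25 × 0.10 × 0.30 = 0.75 subjects, or 1.0 point.
- High: 29 × 0.20 × 0.40 = 2.3 subjects, or 3.2 points.

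The 29 is generous. It is every 4 mg non-success at a 60% rate (72 − 43), including those who drop out and never escalate.

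**7. When the conclusion could turn.** The exact lower limit is 39.31% for 37/72 and 40.65% for 38/72, so at that margin one subject decides. But a 4 mg success normally keeps 4 mg as the last evaluated dose and is therefore also an any-dose success. The any-dose count without the clause can be 37 only if the 4 mg count is 37 or fewer, and then the primary has already missed. At the planned rate, 4 mg successes alone (43/72) give a lower limit of 47.5%. The exception is a 4 mg subject with a seizure after Day 183 but before a late Visit 9 who then escalates.

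**The case against.** The strongest reply is that the sentence was never meant to reach the Extension. It follows a sentence about completers, says that its subjects are also seizure-free, and explains Day 183 as the target date of the week-26 visit. With a ±7-day window, it reads naturally as protecting a subject whose seizure falls between Day 183 and a late Visit 9a. SAP 5.4.2 likewise speaks of the Maintenance Period. This is probably the intent, but SAP 8.2 does not state it, and SAP 5.4.1 sends the reader to Section 8 for the definition of seizure-free status. The reply does bear on the repair: a bare completion requirement could exclude the very subjects the sentence protects, since a seizure after Day 183 but before Visit 9a may itself end Maintenance.

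Few subjects may be affected. Intolerance at 8 mg can first lead to down-titration to 6 mg, from which a subject can still complete. At the early analysis, late escalators will not have reached Day 183. Both points stand. The mid-range effect of about 1 point is small beside an interval about 24 points wide (64.7 − 40.7).

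A reader might infer three stronger things, none of which the documents support.

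- *That the primary analysis is exposed.* The 4 mg sentence also lacks a completion condition. But under Protocol 9.1.2.1 a subject who cannot tolerate 4 mg in Maintenance discontinues the study, so there is no Extension diary to trigger it.
- *That one subject could overturn an otherwise successful trial.* Step 7 shows that this margin arises only after the primary has missed.
- *That the 52-week rate is inflated in the same way.* A Day 240 seizure lies within 52 weeks of Maintenance Day 1 (364 days) and within 26 weeks of an Extension that began about Day 60 (60 + 182 = 242), so that subject fails the 52-week rate anyway.

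Subjects who leave the study altogether are also outside the point. It concerns only early transition to the Extension.

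**Conclusion.** The any-dose definition, as written, scores an early 8 mg leaver with a first seizure after Day 183 as seizure-free and the same leaver without a seizure as non-seizure-free. No other section supplies the missing condition. The result can overstate the key secondary any-dose rate, and analyses that reuse that 26-week status, by 1.4 points per subject at 72 subjects.

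The number of such subjects is unknown and probably small; the 0.2 to 2.3 range rests wholly on assumed percentages. The primary conclusion is untouched if Protocol 9.1.2.1 is followed. The key secondary conclusion could change only where the primary had already missed 40%, and the 52-week rate is little affected. This is a defect in a stated rule, worth correcting before database lock, and not a threat to the trial's main claim.

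**What to change.** In SAP 8.2, replace the late-seizure sentence of the any-dose definition and, for consistency, of the 4 mg definition with wording such as:

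*Subjects whose first seizure after Maintenance Day 1 of the evaluated dose occurred after Day 183 will also be treated as Seizure-Free only if they completed, or were still in, the Maintenance Period of that dose on Day 183. Subjects who left that Maintenance Period before then without meeting the completion definition are non-Seizure-Free, whatever is recorded later.*

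The alternative of still being in Maintenance on Day 183 keeps the protection for a seizure before a late final visit. The cost is this SAP wording and one condition in the derivation program, with no new data. The any-dose rate may come out slightly less favourable.

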#### **9.5.1.3 Efficacy Assessments**

Efficacy will be assessed by seizure counts and types as recorded on the diary.

Diaries will be dispensed to all subjects and returned from all subjects at each visit as described in Table 3. The diary is to be completed by the subject or the caregiver. All seizure counts and types will be recorded. At each visit the subject or the caregiver will be instructed by the site personnel as to how to complete the diary and reminded that they must return the diary at their next scheduled clinic visit and at the Early Discontinuation and Follow-up Visits (if applicable). To ensure correct seizure classification, the medically qualified investigator should review the diary with the subject or the caregiver at all visits. Subjects or caregivers must be counseled if diary compliance is not satisfactory.

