##### 9.7.1.6.2 SECONDARY EFFICACY ANALYSES

The number (percentage) of subjects with POS who achieved seizure-free during the 26-week Maintenance Period regardless of perampanel dose and the corresponding 95% CI will be calculated on the mITT Analysis Set. To examine if the 95% lower CI exceeds the threshold (ie, 40%) is the key secondary efficacy analysis.

The number (percentage) of subjects in the mITT population with POS who achieved seizure-free during the 52-week treatment (ie, 26-week Maintenance Period and 26-week Extension Phase) and the corresponding 95% confidence interval (CI) will be calculated.

Median time to first seizure onset will be estimated by Kaplan-Meier method. Time to first seizure onset will be defined as the time from the first date of Maintenance Period to the date of first seizure onset during the Maintenance Period. Subjects who withdraw from the study before first seizure onset will be censored at the time of study discontinuation.

Median time to withdraw from the study will be estimated by Kaplan-Meier method. Time to withdraw from the study will be defined as the time from the first date of Maintenance Period to the date of discontinuation from the study. Subjects who are ongoing at the data cutoff will be censored at the time of data cutoff.

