5.4.2 Secondary Efficacy Analyses

The number (percentage) of subjects with POS who achieved seizure-free during the 26-week Maintenance Period regardless of perampanel dose and the exact corresponding 95% CI will be calculated. To examine if the 95% lower CI exceeds the threshold (ie, 40%) is the key secondary efficacy analysis. The 26-week Maintenance Period mentioned here is the Maintenance Period of the last evaluated dose (ie, 4 or 8mg).

The number (percentage) of subjects with POS who achieved seizure-free during the 52-week treatment of 4 mg (ie, 26-week Maintenance Period of 4 mg and 26-week Extension Phase) and the corresponding 95% CI will be calculated.

The number (percentage) of subjects with POS who achieved seizure-free during the 52-week treatment (ie, 26-week Maintenance Period and 26-week Extension Phase) and the corresponding 95% CI will be calculated. The 26-week Maintenance Period mentioned here is the Maintenance Period of the last evaluated dose.

Median, Q1 and Q3 time to first seizure onset will be estimated by Kaplan-Meier method. The cumulative probability of the event (ie, seizure occurrence) at every 26 weeks will also be calculated. Corresponding 2-sided 95% CIs will also be presented. Kaplan-Meier estimates of the time to event will be plotted over time. The Follow-up Phase will not be included in this analysis. The above analysis will be summarized for the entire study period of 4 mg and the entire study period of the last evaluated dose, respectively.

Time to first seizure onset will be defined as the period from the first dose of study drug in the Maintenance Period of the last evaluated dose to the first seizure onset. The censoring rule for the analysis of time to first seizure onset will be provide in the [section 8](#).

Median, Q1 and Q3 time to withdraw from the study will be estimated by Kaplan-Meier method. The cumulative probability of the event (ie, withdraw from the study) at every 26 weeks will also be calculated. Corresponding 2-sided 95% CIs will also be presented. Kaplan-Meier estimates of the time to event will be plotted over time. The Follow-up Phase will not be the period to be analyzed. The above analysis will be summarized for the entire study period of 4 mg and the entire study period of the last evaluated dose, respectively.

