Study days during the post-baseline of maintenance period will be the period between the date of study drug dispensing for the Maintenance Period of the last evaluated dose and the disposition data in maintenance period of the last evaluated dose. Study days during the post-baseline of extension phase will be the period between the disposition data in maintenance period of the last evaluated dose and the date of data cutoff or the date of study discontinuation, whichever comes first.

the data on seizure expression that obtained during the Titration Period and the Follow-up Phase will be presented only in the subject data listing.

Handling of missing data

- **Seizure frequency**

If subjects have a missing seizure count in any of each seizure type (ie, simple partial with motor signs, simple partial without motor signs, complex partial, and complex partial with secondarily generalized seizure) for each unique diary record, the overall seizure frequency for that record will be handled as missing data. Similarly, if complex partial and/or complex partial with secondarily generalized seizure are missing for each unique diary record, then complex partial seizure plus secondary generalized seizure frequency will be handled as a missing data.

- **EQ-5D-5L**

No imputation will be performed for the missing value.

Censoring rules for time to event analysis

1. The censored rule for the analysis of time to first seizure onset will be provided in the following table. If subjects met multiple censoring criteria, the censoring date will be the earliest date of them.

No.	Situation	Date of Event or Censoring	Outcome
1	Seizure onset	Date of the first seizure onset	Event
2	Withdraw from the study	Date of study withdrawal	Censored
3	Ongoing at the data cutoff (with no seizure)	Date of data cutoff (each subject's final non-missing assessment date)	Censored

2. The censored rule for the analysis of time to study withdrawal will be provided in the following table. If subjects met multiple censoring criteria, the censoring date will be the earliest date of them.

No.	Situation	Date of Event or Censoring	Outcome
1	Withdraw from the study	Date of study withdrawal	Event
2	Ongoing at the data cutoff	Date of data cutoff (each subject's final non-missing assessment date)	Censored

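### SAP 8.2 has no single end of follow-up: time to withdrawal leaves the protocol's censoring date, and Extension seizure frequency may count days that no diary covers

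*SAP*

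**What the plan says.** **Time to withdrawal.** Protocol 9.7.1.6.2, repeated in the synopsis, states: "Subjects who are ongoing at the data cutoff will be censored at the time of data cutoff". In the second censoring table of SAP 8.2, a withdrawal is an event on the "Date of study withdrawal". For a subject still ongoing, the table gives the data cutoff date followed in parentheses by that subject's "final non-missing assessment date". The table for time to first seizure has the same entry. SAP 5.4.2 sets the output: "The cumulative probability of the event (ie, withdraw from the study) at every 26 weeks will also be calculated". It also asks for quartiles, confidence intervals and plots, and SAP 5.4.3 repeats the analysis by country. SAP section 7, which lists even minor changes from the protocol, does not mention the censoring date.

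**Extension seizure frequency.** On the numerator, SAP 8.2 says: "Post-baseline seizure frequency will be composed of the dispensed diary". Protocol 9.5.1.3 says how diaries arrive: "Diaries will be dispensed to all subjects and returned from all subjects at each visit as described in Table 3". Protocol Table 5 has Extension diaries returned at weeks 6, 12, 18 and 26, then every 12 weeks. The day count in the denominator, however, ends at "the date of data cutoff or the date of study discontinuation, whichever comes first", with no mention of the last assessment.

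**The concern.** The end of follow-up should match what is known about each outcome. Seizures are known only as far as the last returned diary. Withdrawal status can be known up to the cutoff, provided someone checks it. SAP 8.2 appears to use these dates the wrong way round: the shorter date for withdrawal and the longer one for Extension seizure frequency.

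For withdrawal, events keep their actual dates while non-withdrawers are cut back to their last visit, nominally up to 12 weeks earlier in the later Extension. That can overstate a secondary endpoint. For seizure frequency, days with no diary count as seizure-free, which can understate an exploratory endpoint. Because the table entry names two dates, two programmers could also derive different results from the same text.

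**Working it through.** The plan states no figure that depends on either rule, so there is none to reproduce.

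**1. Possible readings of the parenthesis**

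| Reading | Withdrawal | First seizure | Extension frequency |
|---|---|---|---|
| Defines the cutoff throughout the SAP | departs from protocol | sound | ends at last assessment, sound |
| Applies only in the two tables | departs from protocol | sound | runs past last diary |
| Has no effect | matches protocol | credits seizure-free time past last diary | runs past last diary |

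No row is right in all three columns.

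**2. Direction for withdrawal.** The Kaplan-Meier estimate is S(t) = Π(1 − d/n) over event times. When all withdrawals up to the cutoff are known, both rules have the same events d. Under the SAP rule ongoing subjects leave earlier, so each n is equal or smaller. Hence 1 − S(t) is never lower than under the protocol rule.

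**3. Size for withdrawal (simulation).** From the documents: 72 subjects (protocol 9.7.2), the visit schedule (Tables 3 and 5), and a cutoff when all subjects have ended 4 mg Maintenance (SAP section 3). Assumed: uniform accrual over 52 or 78 weeks and a constant withdrawal hazard λ = −ln(1 − p)/52, with p = 25% or 40% a year. Time runs from the start of 4 mg Maintenance; the move to 8 mg is not modelled. True values are 1 − (1 − p)^(t/52): for p = 25%, 25.0% at week 52 and 35.0% at week 78; for p = 40%, 40.0% and 53.5%.

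| Time, accrual | p | Cutoff rule (%) | SAP rule (%) | Difference (points) |
|---|---|---|---|---|
| Week 26, either | both | same | same | 0 |
| Week 52, 52 weeks | 25% | 25.0 | 26.1 | 1.1 |
| Week 52, 52 weeks | 40% | 40.07 | 41.52 | 1.45 |
| Week 52, 78 weeks | 25% | 25.1 | 25.7 | 0.6 |
| Week 52, 78 weeks | 40% | 40.14 | 40.97 | 0.8 |
| Week 78, 78 weeks | 25% | 35.1 | 37.6 | 2.5 |
| Week 78, 78 weeks | 40% | 53.65 | 56.65 | 3.0 |

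Week 26 shows no difference because every subject has passed that point by the cutoff.

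**4. Same simulation, but a withdrawal reaches the database only at the next scheduled visit** (78-week accrual)

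| p | Week | True (%) | SAP rule (%) | Cutoff rule (%) |
|---|---|---|---|---|
| 25% | 52 | 25.0 | 25.1 | 24.6 |
| 25% | 78 | 35.0 | 35.1 | 33.0 |
| 40% | 52 | 40.0 | 40.1 | 39.3 |
| 40% | 78 | 53.5 | 53.6 | 50.8 |

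Here the SAP rule is close to the truth and the cutoff rule reads low.

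**5. Extension frequency for a subject ongoing at the cutoff.** The calculated rate divided by the diary-covered rate equals weeks covered by diary / weeks to cutoff.

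- Cutoff at Extension week 37, last diary at week 26: 26/37 = 0.70. If the diary rate is half of baseline, the true change is −50%, but the formula gives 0.70 × 0.5 − 1 = −65%.
- Cutoff just before the next visit: 0.51 (last diary week 6), 0.67 (week 12), 0.70 (week 18), 0.69 (week 26), 0.76 (week 38).
- Cutoff midway between visits: 0.67 to 0.86 for the same diaries.
- Cutoff before the week 6 visit: no Extension diary has come back, so the formula as written gives 0, a false −100%.

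**The case against.** **The text is ambiguous.** Neither document defines the data cutoff as a calendar date, and protocol 9.7.1 leaves detail to the SAP. A reader might infer that both analyses are certainly wrong. The documents do not support that: if the parenthesis defines the cutoff everywhere, the Extension denominator is sound; if it has no effect, the withdrawal rule agrees with the protocol. What remains is the table in step 1, where no reading serves all three analyses. SAP 5.4 also speaks of what is in the clinical database at the cutoff, which suggests one study-level date.

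**Withdrawal may not be known up to the cutoff.** This objection has real force. Extension visits are up to 12 weeks apart, and protocol 9.5.5 has subjects who stop attending traced afterwards. Step 4 shows that moving to the cutoff without checking status could replace an upward bias with a downward one. The direction in step 2 is a comparison of the two rules, not proof that the SAP rule is further from the truth.

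**A reader might infer an overstatement of 12 to 15 points at week 78.** That arises only with 52-week accrual. Follow-up then ends at 26 + 52 = 78 weeks, and the last scheduled visit is week 76 (Extension week 50). Under last-visit censoring no ongoing subject is at risk after it; the risk set was empty in about 99% of runs. The figure reads the curve beyond its data and should not be used.

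**The effect is small and limited.** The week 52 difference compares with a simulated standard error of about 5 to 6 points. At the end of the study, the End of Study Visit largely aligns last assessment with end of follow-up, so the effect falls mainly at the earlier cut. For seizure frequency, subjects with no Extension seizures score −100% under either denominator; if they are the majority, the median does not move. All of this stands, and it limits the importance of the point.

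**Conclusion.** The point holds as an inconsistency in SAP 8.2, with modest consequences.

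- **Withdrawal.** On either reading that gives the parenthesis effect, the SAP departs from the protocol without logging it. If withdrawals are known up to the cutoff, the overstatement is 0 at week 26 of the 4 mg analysis, about 0.6 to 1.5 points at week 52, and about 2.5 to 3 points at week 78 with 78-week accrual. These sizes rest on assumed accrual and withdrawal rates. If withdrawals are recorded only at the next visit, the SAP rule is close to unbiased. The last-evaluated-dose version was not simulated; subjects still in 8 mg Maintenance at the cutoff could be affected before week 26.
- **Extension frequency.** Unless the parenthesis applies throughout the SAP, the rate is understated for subjects ongoing at the cutoff, by 30% in the example. No population-level effect has been shown.

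A reader might infer that the efficacy conclusion is at risk. It is not: the primary and key secondary comparisons with 40% use neither rule.

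**What to change.** 1. **Extension seizure frequency:** end the day count at the last day covered by a returned diary, or at discontinuation if earlier. Treat a subject with no returned Extension diary as missing, not zero.
2. **Time to withdrawal:** censor ongoing subjects at the calendar data cutoff, as in protocol 9.7.1.6.2, with each subject's status confirmed as of that date from disposition data. Where it cannot be confirmed, censor at the last date the subject was known to be in the study.
3. **Time to first seizure:** keep the last-assessment date, stated without the second date beside it.
4. Define the data cutoff once as a calendar date, and record the choices in SAP section 7.

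The cost is a few lines of SAP wording, one changed derivation, and a status check for ongoing subjects at the cutoff. No visit or procedure is added for subjects.
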